3. PARTICIPANT SELECTION

3.1 Eligibility Criteria

All laboratory tests that are a part of the eligibility criteria must be completed within 14 days prior to the date of registration. Diagnostic tests that are a part of the eligibility criteria must be performed within 30 days of the date of registration. Participants must meet the following criteria on screening examination to be eligible to participate in the study:

- 3.1.1 Study participants must have histologically confirmed primary malignant bone tumor in the sacrum for which surgery and radiation or radiation alone are planned.

CONFIDENTIAL

This document is confidential. Do not disclose or use except as authorized.

- 3.1.2 Age 18 years or older. In children under the age of 8, tetracycline derivatives have been reported to stain tooth enamel yellow color. These considerations lead us to exclude young persons under the age of 18 from the study.
- 3.1.3 Participants in the surgical arm must have normal organ and marrow function as defined below:
- Total bilirubin within normal institutional limits
 - AST (SGOT)/ALT (SGPT) < 2.5 X institutional upper limit of normal
 - Creatinine within normal institutional limits or creatinine clearance > 60 mL/min/1.73 m² for subjects with creatinine levels about institutional normal limit
- 3.1.4 The effects of tetracyclines and radiation used in computer tomography on the developing human fetus are known to be detrimental. For this reason, women of child-bearing potential and men must agree to use adequate contraception (hormonal or barrier method of birth control; abstinence) prior to study entry and until after the last study related computer tomography scan . Should a woman become pregnant or suspect she is pregnant while participating in this study, she should inform her treating physician immediately.
- 3.1.5 Ability to understand and willingness to sign a written informed consent.

3.2 Exclusion Criteria

Participants who exhibit any of the following conditions at screening will not be eligible for admission into the study.

- 3.2.1 Participants who have had surgery, chemotherapy, or radiotherapy of the sacrum prior to entering the study
- 3.2.2 History of allergic reactions attributed to compounds of similar chemical or biologic composition to tetracyclines.
- 3.2.3 Pregnant or nursing
- 3.2.4 Uncontrolled inter current illness including, but not limited to ongoing or active infection, symptomatic congestive heart failure, unstable angina pectoris, cardiac arrhythmia, or psychiatric illness/social situations that would limit compliance with study requirements.

3.3 Inclusion of Women, Minorities and Other Underrepresented Populations

We will not restrict subject selection by race, gender, or age group. The external validity of the results obtained in this study would benefit from population diversity. Since the study aims at improving outcomes for all patients with bone tumors, exclusion of any group that can be affected by the disease can result in the failure to collect clinically important information.

CONFIDENTIAL

This document is confidential. Do not disclose or use except as authorized.

4. REGISTRATION PROCEDURES

4.1 General Guidelines for DF/HCC and DF/PCC Institutions

Institutions will register eligible participants with the DF/HCC Quality Assurance Office for Clinical Trials (QACT) central registration system. Registration must occur prior to the initiation of therapy. Any participant not registered to the protocol before treatment begins will be considered ineligible and registration will be denied.

A member of the study team will confirm eligibility criteria and complete the protocol-specific eligibility checklist.

Following registration, participants may begin participation in the protocol. Issues that would cause delays should be discussed with the Principal Investigator. If a participant does not participate in the protocol following registration, the participant's protocol status must be changed. Notify the QACT Registrar of participant status changes as soon as possible.

4.2 Registration Process for DF/HCC and DF/PCC Institutions

The QACT registration staff is accessible on Monday through Friday, from 8:00 AM to 5:00 PM Eastern Standard Time.

The registration procedures are as follows:

1. Obtain written informed consent from the participant prior to the performance of any study related procedures or assessments.
2. Complete the protocol-specific eligibility checklist using the eligibility assessment documented in the participant's medical/research record. **To be eligible for registration to the study, the participant must meet each inclusion and exclusion criteria listed on the eligibility checklist.**

Reminder: Confirm eligibility for ancillary studies at the same time as eligibility for the treatment study. Registration to both treatment and ancillary studies will not be completed if eligibility requirements are not met for all studies.

3. Fax the eligibility checklist(s) and all pages of the consent form(s) to the QACT at [contact].
4. The QACT Registrar will (a) validate eligibility and (b) register the participant on the study.
5. The QACT Registrar will send an email confirmation of the registration to the person initiating the registration immediately following the registration.

[figure not shown]
5. TREATMENT PLAN

CONFIDENTIAL

This document is confidential. Do not disclose or use except as authorized.

Study participants will receive treatment as determined by their treating physicians at the Massachusetts General Hospital for Malignant Bone Tumors of the Sacrum. This may be radiation alone or pre-operative radiation therapy followed by surgery. The treatment plan including MRI and CT imaging is determined by the clinical situation and not by the study. Patients planned for surgery typically receive pre-operative MRI of their pelvis and/or sacrum. In addition, patients often receive a pelvic or sacral computed tomographic image. A CT of the chest is performed to evaluate for pulmonary metastasis. Figure 9 outlines the current standard radiation treatment options. Study participants may also receive radiation therapy as part of another clinical trial. For surgical candidates, the standard treatment includes pre-operative radiation of 50.4 Gy, followed by a recovery period of approximately 4 to 5 weeks. Surgery involves removing the malignant tumor in the sacrum in one piece, preferably with a cuff of normal tissue around the tumor. After approximately 6 weeks of recovery, to allow the surgical incision to heal, the patient is treated with another 19.8 Gy up to 27 Gy of radiation postoperatively depending on the final margin status (higher for gross residual disease), as outlined in Figure 9(A). If the wound is not healed or there is another medical reason to delay adjuvant radiation, then radiation may begin later. The patients are typically followed every 3 months with an MRI of the pelvis/sacrum to evaluate for a local recurrence. A CT scan is often ordered if there is a concern for a fracture. In addition, patients typically receive a chest x-ray at 3 months and 9 months after surgery. A chest CT is ordered at 6 months and 12 months after surgery. The same protocol is used during the second year of follow up. Non-surgical candidates receive 72 up to 77.4 Gy of radiation depending on the histology (72 Gy for osteosarcoma and chondrosarcoma and 77.4 Gy for chordoma) as outlined in Figure 9 (B).

Figure 9: Radiation Treatment Flowchart

CONFIDENTIAL

This document is confidential. Do not disclose or use except as authorized.

5.1 Pre-treatment Criteria

Not applicable, as long as labs are within normal limits (see Section 3.1.3)

5.2 Bone Labeling Drug Administration

For participants in the non-surgical arm, no bone labeling drugs are administered. These participants will receive a standard radiation regimen with blood samples and imaging (QCT) only as their participation in this study. For participants in the surgical arm, the bone labeling drugs are described below.

5.2.1 *Demeclocycline*

Participants in the surgical arm will self-administer the first label set; demeclocycline 150 mg PO QID (daily dose 600 mg) during 2 periods of 3 days, starting day 18 and day 3 prior to the start of their scheduled pre-operative radiotherapy. Participants will be given a drug diary (Appendix 1) to keep a record of the dosing. Demeclocycline comes in a form of an oral pill and does not require any special equipment for administration. It has a well-established safety profile with minimal adverse effects. No observation period or vital signs monitoring is required. Demeclocycline should be administered 1 hour before or 2 hours after food or milk, with adequate amounts of fluid to decrease the risk of esophageal irritation and ulceration. If a dose is vomited, the participant should contact the research coordinator, so we can provide an extra dose. Contact information will be provided in the drug diary.

5.2.2 *Tetracycline*

Participants in the surgical arm will also self-administer the second label set; tetracycline 250mg PO QID (daily dose 1000 mg) during 2 periods of 3 days, starting day 24 and day 9 prior to their scheduled surgery. Participants will be given a drug diary (Appendix 1) to keep a record of the dosing. Tetracycline comes in a form of an oral capsule and does not require any special equipment for administration. It has a well-established safety profile with minimal adverse effects. No observation period or vital signs monitoring is required. Tetracycline should be administered on an empty stomach: 1 hour prior to meals, or 2 hours after meals. If a dose is vomited, the participant should contact the research coordinator, so we can provide an extra dose. Contact information will be provided in the drug diary.

5.3 Other Studies

As outlined in section 8.3.

5.4 Definition of Dose-Limiting Toxicity

N/A

5.5 General Concomitant Medication and Supportive Care Guidelines

CONFIDENTIAL

This document is confidential. Do not disclose or use except as authorized.

Patients may receive all concomitant therapy deemed necessary to provide adequate support for any standard treatment or study related events.

5.6 Duration of Therapy

Standard treatment will continue for study participants as long as clinically indicated until the standard treatment is completed. As noted above, participants in the radiation arm will provide blood samples for up to 6 months after completion of radiation therapy. Participants in the surgical arm will self administer the bone labeling drugs as described above and will provide blood samples for up to 6 months after completing radiation therapy.

5.7 Duration of Follow Up

Participants will be followed for radiographic and/or clinical evidence of fracture and assessment of quality of life for 12 months after their surgery/radiotherapy or until death, whichever occurs first. Participants removed from study for unacceptable adverse events will be followed until resolution or stabilization of the adverse event.

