1. OBJECTIVES

1.1 Study Design

This is a pilot study designed to characterize the effects of high energy radiation on human bone degradation, with a specific interest in reducing the rate of sacral fractures.

Figure 1: Phase Transition into Clinical Trials

Based on the data published in animal models, we hypothesized that bone degradation after irradiation is associated with clinically detectable changes in serum markers, bone density, and bone architecture. This study is a step towards better characterizing those changes in humans, and understanding the mechanism of the underlying pathology. The results of this research may ultimately lead to the development of interventions aimed at reducing the burden of radiation-induced fractures, as outlined in Figure 1:

Figure 2 provides a succinct layout of the proposed experimental plan and a summary of the data we expect to collect.

Figure 2: Experimental Design Summary

In vivo (patient labs + imaging)	In vitro (bone biopsies)	Experimental Design. We plan to conduct in vivo and in vitro studies to characterize radiation-induced changes in bone. We will look at changes in the cellular composition of bone, bone metabolism, microscopic architecture, and mechanical properties.

 ▪ Serum markers ▪ QCT 	
 ▪ Undecalcified histology ▪ Tetracycline double staining ▪ Micro-CT ▪ Electron scattering microscopy ▪ Nanoindentation 	

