9. STUDY CALENDAR

9.1.1 Non-Surgical Arm Study Calendar

Time point	Visit 1	Visit 2	Visit 3	Visit 4	Visit 5	Final visit
	Screening	Start RT Baseline	Halfway RT ~3.5 Weeks	End of RT ~7 Weeks	~3Months after RT	~6 Months after RT
Medical History	X					
Study Blood test		X	X	X	X	X
CT scan		X			X	
Pregnancy Test	X					

RT = radiotherapy

* Study visit are dependent on treatment events like start/end of pre- or post-op radiotherapy and surgery. Therefore treatment delay will result in delay of study visits.

CONFIDENTIAL

This document is confidential. Do not disclose or use except as authorized.

9.1.2 *Surgical Arm Study Calendar*

	Visit 1	Visit 2	Visit 3	Visit 4	Visit 5	Visit 6	Visit 7	Visit 8	Final Visit
	Before Surgery				Surgery Week		After post-op RT	Follow-Up	
	Screening	Start RT Baseline	End RT ~5.5 Weeks	3-5 days before surgery	Surgery stage 1	Surgery stage 2	End post-op RT	1 month after post-op RT	4 months after post-op RT
Medical History	X								
Eligibility blood test	X								
CT scan		X		X					
Study Blood test		X	X				X	X	X
Bone Biopsy					X	X			
Dispense drugs	X		X						
Pregnancy Test	X								

RT = radiotherapy

* Cycle 1 drugs will be taken between visit 1 and 2. Cycle 2 drugs will be taken between visit 3 and 4*
 Study visit are dependent on treatment events like start/end of pre- or post-op radiotherapy and surgery.
 Therefore treatment delay will result in delay of study visits.

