14.4 Analysis of Secondary Endpoints

Paired t-test and Wilcoxon signed-rank test will be performed on the differences between the two groups in the average values of PROMIS T scores. A P-value of 0.05 will be considered to be statistically significant. Spearman and Kendall rank correlations will be used to measure the strength of dependence between the bone mineral density and exploratory variables whenever possible.

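### Section 5.7 promises 12 months of fracture and quality-of-life follow-up and section 14.4 tests PROMIS scores, but neither study calendar schedules a quality-of-life assessment or a study contact as late as 12 months

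*Combined protocol and SAP*

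**What the plan says.** Section 5.7 makes a commitment for every participant, which ends early only if the participant dies: "Participants will be followed for radiographic and/or clinical evidence of fracture and assessment of quality of life for 12 months after their surgery/radiotherapy".

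Section 14.4, headed as the analysis of secondary endpoints, specifies: "Paired t-test and Wilcoxon signed-rank test will be performed on the differences between the two groups in the average values of PROMIS T scores". It adds: "A P-value of 0.05 will be considered to be statistically significant".

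Section 9 gives one calendar per arm. The final non-surgical visit (9.1.1) is at about "6 Months after RT", and the final surgical visit (9.1.2) is at "4 months after post-op RT". The rows cover medical history, blood tests, CT and a pregnancy test. The surgical calendar adds biopsy and drug dispensing.

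Section 1.1 describes the study as one "with a specific interest in reducing the rate of sacral fractures". Section 2.1 explains that the radiation-only arm is included because it is unclear how far surgery contributes to fractures.

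**The concern.** The follow-up section, the calendars and the analysis section do not describe the same study. Site staff work from the calendars, and these ask for no questionnaire at any visit. The analysis section nevertheless says that questionnaire scores will be tested. A PROMIS score not taken before radiotherapy cannot be recovered later, so change from baseline would be lost for good.

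For fracture, the promised window runs to 12 months while scheduled study contact stops well before that. Fracture is the clinical problem that motivates the work. Section 2.4.1 also expects serum-marker changes to come before fractures, which can only be examined if fracture dates are recorded.

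The PROMIS test has a second defect. It applies paired methods to a difference between two groups made up of different patients.

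**Working it through.** **The plan's own figures.** The only power figures (section 14.2) concern bone density: 0.942, 0.807 and 0.469 at n = 30, 20 and 10. A two-sided paired t-test at alpha 0.05, with noncentrality (10/15) × √n and n − 1 degrees of freedom, gives 0.9416, 0.8073 and 0.4692. They reproduce, and nothing below depends on them.

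**Is quality of life scheduled?** A row-by-row reading gives:
- Non-surgical calendar: 0 of 6 visits.
- Surgical calendar: 0 of 9 visits.
- PROMIS is also absent from the objectives (1.2, 1.3), the endpoints (14.1.1, 14.1.2), the special studies (8.3) and the measurement list in Appendix 3. In the supplied text it is named only in section 14.4.

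**How far do the calendars reach?** Inputs:
- About 6 weeks from surgery to post-operative radiotherapy (section 5).
- Post-operative dose 19.8 to 27 Gy (section 5).
- Final surgical visit 4 months after post-operative radiotherapy; final non-surgical visit about 6 months after radiotherapy (section 9).
- One month = 52.18/12 = 4.35 weeks.

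The documents do not state how long post-operative radiotherapy lasts. I assume the pre-operative pace continues: 50.4 Gy in about 5.5 weeks is 50.4/5.5 = 9.2 Gy per week. Then 19.8/9.2 = 2.2 weeks and 27/9.2 = 2.9 weeks. Assuming 1.8 Gy fractions five times a week gives 11/5 = 2.2 and 15/5 = 3.0 weeks. I use 2.2 to 3.0.

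Surgical arm, from surgery: (6 + 2.2)/4.35 + 4 = 5.9 months, up to (6 + 3.0)/4.35 + 4 = 6.1 months.

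Section 5.7 does not say exactly when its 12 months start, so the shortfall is shown for each possible anchor:

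| Anchor | Last study visit | Short of 12 months by |
|---|---|---|
| Non-surgical, end of radiotherapy | 6 months | 6 months |
| Non-surgical, start of radiotherapy (plus 7 to 8.5 weeks) | 7.6 to 8.0 months | 4.0 to 4.4 months |
| Surgical, end of post-operative radiotherapy | 4 months | 8 months |
| Surgical, surgery | 5.9 to 6.1 months | about 6 months |
| Surgical, start of radiotherapy | 8.3 to 8.7 months | 3.3 to 3.7 months |

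The last row adds 5.5 weeks of radiotherapy, 4 to 5 weeks of recovery and 1 week for the staged surgery to the interval from surgery. All rows assume no treatment delay. No anchor reaches 12 months.

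**What would capture fracture?**
- Up to the last visit: sections 6, 11.1.1 and 11.2 require adverse events to be assessed at evaluation visits and recorded until the final study visit. A clinically evident fracture falls within that definition.
- Study imaging: in the surgical arm the second and last QCT is before surgery (8.3.2), so it cannot show a post-operative fracture.
- After the last visit: section 5 describes usual-care MRI about every 3 months, aimed at recurrence, and CT when fracture is suspected. It says clinical need, not the study, determines this imaging.
- Follow-up form: section 12.1.2 ties it to a follow-up visit or call defined in the protocol, and none is defined at 12 months.

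**The case against.** The best defence has four parts.

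*Fracture data would still arise.* This is largely right. Adverse-event recording covers clinically evident fractures up to the final visit, usual-care imaging continues beyond it, and section 5.7 asks only for radiographic and/or clinical evidence. A reader might infer that fracture would go unrecorded, or that patients have no contact for half the year. The documents support neither reading. What is missing is a scheduled study contact, or an instruction to extract records, between the last visit and 12 months.

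*Ascertainment need not differ by arm.* A reader might also infer that chance detection would bias the comparison of arms. CT ordered on suspicion implies variation between patients, but nothing cited shows that routine sacral imaging differs by arm.

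*The schedule may be in text not supplied.* The contents page lists a quality-of-life survey appendix that is not in the supplied text, and section 8.3.1 refers to a schema that is not visible. I give the missing appendix no weight. The point rests on the two calendars, which are shown in full, and on their disagreement with sections 5.7 and 14.4. If a schedule exists elsewhere, it still has to appear in the calendars.

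*Fracture need not be an endpoint.* I agree. In a 30-patient pilot meant to characterise bone changes, leaving fracture out of the endpoints is a legitimate choice and not an error.

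**Conclusion.** The inconsistency is real and should be corrected. As scheduled, none of the planned 30 participants has a PROMIS assessment at any visit, so the test in section 14.4 has no scheduled data and no baseline. Study contact ends 6 months short of 12 after radiotherapy in the non-surgical arm. In the surgical arm it ends 8 months short after post-operative radiotherapy, or about 6 months short counted from surgery. The surgery-based figure assumes 2 to 3 weeks of post-operative radiotherapy and no delays.

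For fracture the conclusion is narrower: later fractures are unscheduled for ascertainment, but they are not unobtainable. A reader might take this as a threat to the main result. It is not one, because the primary bone-density endpoint and its power use neither PROMIS nor fracture data.

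**What to change.** Reconcile sections 5.7, 9 and 14.4 by one of two routes.

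(a) Keep the commitment.
- Add PROMIS to both calendars at baseline, before radiotherapy, and at a follow-up time defined the same way in both arms, for example 12 months from a stated anchor. The existing final visits are unsuitable as the common time, because they fall at different intervals after radiotherapy in the two arms.
- Add a 12-month call or chart review that records fracture (yes/no, date, imaging source).
- List PROMIS as an exploratory endpoint in 14.1.2.
- In 14.4, use paired tests only for within-patient change, and an unpaired test (two-sample t or Mann–Whitney) between arms.
- Making fracture a formal endpoint is optional.

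(b) Drop it. Delete the PROMIS analysis from 14.4 and shorten the follow-up in 5.7 to what the calendars deliver.

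Route (a) costs a short questionnaire at two times and one remote contact per patient, which sections 5.7 and 12.1.2 already imply. Route (b) costs only wording, but gives up quality-of-life data and fracture follow-up to 12 months. Neither changes the sample size or adds study imaging.

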5.8 Criteria for Removal from Study

Participants will be removed from study if any of the adverse events listed in section 6.2.2 or 6.1.2 occur. The reason for study removal and the date the participant was removed must be documented in the study-specific case report form (CRF). Alternative care options will be discussed with the participant.

In the event of unusual or life-threatening complications, participating investigators must immediately notify the Principal Investigator, [name] at [contact] or MGH [name]

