6. EXPECTED TOXICITIES AND DOSING DELAYS/DOSE MODIFICATIONS

If possible, symptoms will be managed symptomatically. In the case of toxicity, appropriate medical treatment will be used (including anti-emetics, anti-diarrheals, etc.).

All adverse events experienced by participants will be collected from the time of the first dose of study treatment, through the study and until the final study visit. Participants continuing to experience toxicity at the off study visit may be contacted for additional assessments until the toxicity has resolved or is deemed irreversible.

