6.1 Anticipated Toxicities

All drugs in this study have been in routine clinical use for many years, and are associated with rare adverse effects. Additional radiation exposure is less than the yearly natural background radiation in the US. A list of the adverse events and potential risks associated with the drugs administered in this study appear below and will determine whether dose delays and modifications will be made or whether the event requires expedited reporting **in addition** to routine reporting.

CONFIDENTIAL

This document is confidential. Do not disclose or use except as authorized.

6.1.1 *Adverse Event List for Tetracycline*

Significant Adverse Reactions (Rare):

- Cardiovascular: Pericarditis
- Central nervous system: Bulging fontanel in infants, increased intracranial pressure, paresthesia, pseudotumor cerebri
- Dermatologic: Exfoliative dermatitis, photosensitivity, pigmentation of nails, pruritus
- Gastrointestinal: Abdominal cramps, anorexia, antibiotic-associated pseudomembranous colitis, diarrhea, discoloration of teeth and enamel hypoplasia (young children), esophagitis, nausea, pancreatitis, staphylococcal enterocolitis, vomiting
- Hematologic: Thrombophlebitis
- Hepatic: Hepatotoxicity
- Renal: Acute renal failure, azotemia, renal damage
- Miscellaneous: Anaphylaxis, candidal superinfection, hypersensitivity reactions, superinfection

Contraindications: Hypersensitivity to demeclocycline, tetracyclines, or any component of the formulation

Concerns related to adverse effects:

- Increased blood urea nitrogen (BUN): May be associated with increases in BUN secondary to antianabolic effects; use caution in patients with renal impairment.
- Photosensitivity: May cause photosensitivity; discontinue if skin erythema occurs. Use skin protection and avoid prolonged exposure to sunlight; do not use tanning equipment.
- Pseudotumor cerebri: Has been (rarely) reported with tetracycline use; usually resolves with discontinuation.
- Superinfection: Prolonged use may result in fungal or bacterial superinfection, including *C. difficile*-associated diarrhea (CDAD) and pseudomembranous colitis; CDAD has been observed >2 months postantibiotic treatment.

Disease-related concerns:

- Hepatic impairment: Use with caution in patients with hepatic impairment; dose adjustment and/or adjustment to interval frequency recommended. Hepatotoxicity and hepatic failure have been reported rarely with use.

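### Section 5.8 removes participants for any listed demeclocycline event, however mild; this contradicts the vomited-dose rule in 5.2.1 and could needlessly cost a surgical patient's QCT pair (minor)

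*Combined protocol and SAP*

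**What the plan says.** The removal rule is in 5.8: "Participants will be removed from study if any of the adverse events listed in section 6.2.2 or 6.1.2 occur". It carries no grade, attribution or time limit. Section 6.1.2 is the adverse event list for demeclocycline. Its heading calls the reactions significant and rare, but its entries include nausea, vomiting, diarrhea, anorexia, headache and dizziness.

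Other sections deal with the same kinds of event:

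- **5.2.1 (and 5.2.2):** "If a dose is vomited, the participant should contact the research coordinator, so we can provide an extra dose".
- **6.2.2:** for the on-treatment symptom items, the patient is told to stop demeclocycline and contact the study team. Leaving the study is not mentioned.
- **6:** "If possible, symptoms will be managed symptomatically".
- **6.1:** the lists "will determine whether dose delays and modifications will be made or whether the event requires expedited reporting".
- **5.7:** "Participants removed from study for unacceptable adverse events will be followed until resolution or stabilization of the adverse event".

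Demeclocycline is taken only in the surgical arm, "during 2 periods of 3 days, starting day 18 and day 3 prior to the start of their scheduled pre-operative radiotherapy". Section 8.3.2 places the first QCT before radiation begins. In the surgical arm the second is just before surgery, about 10 weeks later, because instrumentation then makes the analysis impossible.

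**The concern.** Section 5.8 is where the protocol sets its removal criteria, so staff will look there first. A coordinator told of one vomited demeclocycline dose is instructed by 5.2.1 to replace it and by 5.8 to take the patient off study. Both cannot be followed.

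The primary endpoint (14.1.1) is a change between two QCT scans, so a patient counts only with both. QCT does not use the fluorescent label. A mild side effect of a labeling drug is therefore no scientific reason to lose the scans, and in the surgical arm a missed second scan cannot be recovered.

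**Working it through.** **1. The texts side by side**

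- *5.2.1 against 5.8: direct conflict.* Vomiting is listed in 6.1.2. One section replaces the dose and continues; the other removes the participant.
- *6.2.2 against 5.8: poor fit, not contradiction.* Telling the patient to stop the drug and call can be followed by the team removing the patient.
- *Section 6 and 5.7: weaker evidence of a narrower intent.* Treating a symptom does not exclude removal. The term unacceptable in 5.7 is undefined and could simply mean the events in 5.8.
- *6.1: weak evidence.* It ties the lists to dose changes and reporting, but 6.3 marks dose modifications as not applicable.

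**2. Which scan is at risk**

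Demeclocycline days are 18, 17, 16 and 3, 2, 1 before radiotherapy (7.2.8), which is 2 × 3 = 6 days. All precede the baseline scan on Day 1. An acute reaction on those days would usually cost the whole pair.

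Losing the second scan alone needs a later listed event. If attribution is not required, the exposed period runs from the first dose (Section 6: "All adverse events experienced by participants will be collected from the time of the first dose of study treatment") to the second scan: 18 + 70 = about 88 days, of which 6 are demeclocycline days. That figure holds only on the non-attributed reading.

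**3. The plan's power, reproduced**

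Inputs from 14.2: change 10 mg/mL, SD of change 15 (printed in mg/dL, read as mg/mL), alpha 0.05. Sidedness is not stated; a two-sided test reproduces the figures.

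Power = P(|T| > t(0.975, n−1)), where T is noncentral t with n−1 degrees of freedom and noncentrality (10/15)·√n.

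| n | Stated | Computed |
|---|---|---|
| 30 | 0.942 | 0.9416 |
| 20 | 0.807 | 0.8073 |
| 10 | 0.469 | 0.4692 |

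**4. Effect of lost pairs**

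95% CI half-width for the mean change = t(0.975, n−1)·15/√n.

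| Surgical pairs | Power | Half-width (mg/mL) |
|---|---|---|
| 20 | 0.807 | 7.0 |
| 19 | 0.785 | 7.2 |
| 18 | 0.760 | 7.5 |

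**5. Effect at assumed removal rates**

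No event rate is given, so the removal rate p is an assumption. Average power is taken over a Binomial(20, 1−p) number of pairs. The chance of losing at least one pair is 1 − (1−p)^20.

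| p | Average power | At least one pair lost |
|---|---|---|
| 1% | 0.803 | 18% |
| 2% | 0.798 | 33% |
| 5% | 0.784 | 64% |
| 10% | 0.758 | 88% |

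Average power falls by 1 point at p = 2.2% and by 5 points at p = 10.1%. This takes removals as independent, each one as costing the pair, and all other surgical patients as having both scans.

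**The case against.** The strongest reply is that 5.8 was meant narrowly and that removal after a drug reaction is a defensible caution. The list is titled for demeclocycline and headed as rare, significant reactions, and 6.1 introduces it as events associated with the study drugs. On that reading, nausea from radiotherapy would not trigger removal. This has force as to intent, but 5.8 does not say it, and even the attributed reading still removes a patient whose demeclocycline caused one vomited dose.

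Several stronger readings are tempting and are not supported:

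- *That 5.8 contradicts every other section on toxicity.* Only 5.2.1 is in direct conflict; the others can be read alongside it.
- *That the catch-all for other worrying symptoms in 6.2.2 is itself a removal criterion.* It is a warning sign under the diabetes insipidus item, not a listed event. The breadth comes from 6.1.2.
- *That the typical harm is loss of the second scan over an 88-day window.* This requires ignoring attribution. An acute demeclocycline reaction falls before baseline.
- *That removed patients are barred from the scan.* No section says so. Section 5.7 gives them follow-up of the event but does not say that nothing else is done.
- *That the primary test is seriously underpowered as a result.* No stated rate supports this. Section 6.1.2 does call diabetes insipidus dose-dependent and common with use, but exposure here is two 3-day courses.

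The cross-reference may also be faulty: 5.8 omits the tetracycline sections 6.1.1 and 6.2.1, and 6.2.1 carries a stray 6.1.2. That is a further reason to correct 5.8.

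**Conclusion.** The concern holds as a minor defect. An operative, mandatory rule reaches mild events without grade or attribution limits and contradicts 5.2.1 on vomiting. Applied literally, it could cost a surgical patient the whole QCT pair or, for a later event if attribution is not required, the second scan. Both consequences rest on the inference that a removed participant has no further study scans.

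The expected effect on the primary test is small. One lost pair lowers power from 0.807 to 0.785. At assumed removal rates of 1% and 2% the average loss is 0.5 and 0.9 points. The main cost is the avoidable loss of an individual patient's scan data in a 20-patient arm.

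**What to change.** Amend 5.8 to separate stopping a drug from leaving the study:

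- A listed event attributed to a labeling drug leads to stopping that drug under 6.2.1 or 6.2.2.
- After hypersensitivity, or any other event that contraindicates tetracyclines, both labeling drugs stop permanently. Section 6.1.1 already lists this contraindication for tetracycline: "Hypersensitivity to demeclocycline, tetracyclines, or any component of the formulation".
- The participant stays on study for QCT, blood draws and follow-up, and for biopsies if judged safe, unless consent is withdrawn or the investigator judges the remaining procedures unsafe.
- The reference in 5.8 is extended to 6.1.1 and 6.2.1.
- An isolated vomited dose is handled under 5.2.1.

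The cost is a short amendment with no new visits or procedures. The downside is that a patient whose drug is stopped loses label-based histomorphometry.
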